9.3 Examination Procedures

Procedures to be performed at each study visit with regard to the study objectives are detailed in [Appendix 2: Examination Procedures, Tests, Equipment, and Techniques](#).

Visit 1 — Screening and Baseline Evaluations (-28 to -1 days prior to surgery)

- Informed consent/assent
- Demographic data
- Medical and medication history
 - Current underlying conditions, including those that began within the last 30 days, which may have been resolved before Visit 1 (Day -1 to Day -28 [prior to surgery]), must be recorded.
 - Any medications the subject is taking, as well as those the subject may have taken but discontinued within 30 days prior to Visit 1 (Day -1 to Day -28 [prior to surgery]) must be recorded.
- Urine pregnancy test (if applicable)
- Inclusion/exclusion criteria
- Ocular pain (study eye only)
- Pin-hole VA
- Slit lamp biomicroscopy

- Ocular inflammation assessment of the anterior chamber cell and flare (study eye only)
- IOP
- Dilated indirect ophthalmoscopy

Visit 2 — Day 1 (18 to 30 hours post-surgery)

- Review inclusion/exclusion criteria
- Medical and medications update
- Ocular pain (study eye only)
- Pin-hole VA
- Slit lamp biomicroscopy
- Ocular inflammation assessment of the anterior chamber cell and flare (study eye only)
- Randomization
- Dose and dispense study medication and dosing diary
- Query for AEs

Visit 3 — Day 2 (Telephone Call)

- Ocular pain (study eye only)

Visit 4 — Day 4 (\pm 1 day window)

- Medical and medications update
- Ocular pain (study eye only)
- Pin-hole VA
- Slit Lamp Biomicroscopy
- Ocular inflammation assessment of the anterior chamber cell and flare (study eye only)
- IOP
- Query for AE

Visit 5 — Day 8 (\pm 1 day window)

- Medical and medications update
- Ocular pain (study eye only)
- Pin-hole VA
- Slit lamp biomicroscopy
- Ocular inflammation assessment of the anterior chamber cell and flare (study eye only)

- IOP
- Query for AEs

Visit 6 — Day 15 (± 2 day window)

- Medical and medications update
- Ocular pain (study eye only)
- Pin-hole VA
- Slit lamp biomicroscopy
- Ocular inflammation assessment of the anterior chamber cell and flare (study eye only)
- IOP
- Query for AEs

Visit 7 — Day 22 (± 2 day window)

- Urine pregnancy test (if applicable)
- Medical and medications update
- Ocular pain (study eye only)
- Pin-hole VA
- Slit lamp biomicroscopy
- Ocular inflammation assessment of the anterior chamber cell and flare (study eye only)
- IOP

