3.1 General Study Design

This study is a multi-center, randomized, double-masked, placebo (vehicle)-controlled study, designed to evaluate the efficacy and safety of OCS-01 ophthalmic suspension (QD versus BID) compared to placebo in treating inflammation and pain following cataract surgery.

Eligible subjects will be randomized [REDACTED] to receive OCS-01 QD, OCS-01 BID, or placebo BID. Subjects will dose 1 drop in the study eye BID for 14 days, beginning 1 day post-surgery in the operated eye. The study will last 20-52 days, including screening and a follow-up visit at Visit 7 (Day 22 ± 2).

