8.2 Missing or Inconclusive Data Handling

8.2.1 PARTIAL DATES

Imputation of partial or missing dates will be conducted in order to classify data as treatment-emergent or concomitant with treatment. Partial/missing start and end dates for AEs and concomitant medications will be imputed as follows:

Partial/missing start date:

- Dates with missing day only will be imputed as the 1st of the month unless the month and year are same as the month and year of first dose of study medication, in which case missing day will be imputed as the first dose day of study medication.
- Dates with both day and month missing will be imputed as 01-Jan unless the year is same as the year of first dose of study medication, in which case missing day and month will be imputed as the first dose day and month of study medication.
- Completely missing dates will be imputed as the first dose date of study medication unless the end date is on or before the first dose date of study medication, in which case missing date will be imputed as 1 Jan of the same year as the end date.

Partial/missing end date:

- Dates with missing day only will be imputed as the last day of the month unless the month and year are the same as the month and year of the last dose of study medication, in which case missing day will be imputed as the last dose day of study medication.
- Dates with both day and month missing will be imputed as 31 Dec unless the year is same as the year of the last dose of study medication, in which case missing day and month will be imputed as the last dose day and month of study medication.
- If the ongoing flag is missing or “Yes” then the date will not be imputed. If ongoing is “No” then the missing end date will be imputed as the last dose date.

The original dates will be displayed in data listings and the imputed dates will be used in derivations only (study day, treatment-emergence status, etc).

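### SAP 8.2.1 imputes end dates without checking the start date or the Visit 1 record, so a medication already stopped can appear to run into treatment, and a record starting after the last dose can end before it begins

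*SAP*

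**What the plan says.** SAP 8.2.1 opens with its purpose: "Imputation of partial or missing dates will be conducted in order to classify data as treatment-emergent or concomitant with treatment". It adds that listings show the original dates and that imputed dates serve derivations such as study day.

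The end-date rule has three bullets:

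- **Day missing:** last day of the month, unless that is the last-dose month, "in which case missing day will be imputed as the last dose day of study medication".
- **Day and month missing:** 31 December, unless that is the last-dose year, "in which case missing day and month will be imputed as the last dose day and month of study medication".
- **Fully missing:** if the ongoing flag is missing or Yes, "then the date will not be imputed"; if it is No, "then the missing end date will be imputed as the last dose date".

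None of the three refers to the record's start date or to Visit 1. On the start side, the bullet for a completely missing date does look across: it applies "unless the end date is on or before the first dose date of study medication". The other two start-date bullets do not.

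Two other provisions determine which records meet these rules. Protocol 9.3 requires Visit 1, held 28 to 1 days before surgery, to record current medications and "those the subject may have taken but discontinued within 30 days prior to Visit 1". SAP 3.1 says "Subjects will dose 1 drop in the study eye BID for 14 days, beginning 1 day post-surgery", with follow-up to Visit 7 on Day 22 ± 2.

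**The concern.** The design itself produces two kinds of record that the end-date bullets do not fit.

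1. **Medications stopped before screening.** If the stop date is absent and the ongoing flag is No, the stop becomes the last dose date. If the start is also absent, the start rule supplies the first dose date, because no pre-dose end date exists to trigger its check. A drug known to have stopped before surgery then spans the whole dosing period.
2. **Events or medications starting after the last dose.** These are collected for about a week after dosing. They are collected for longer after an early stop of study drug, since Protocol 6.6 and 9.6.2 keep such subjects in the visits. With a known start and an incomplete stop, the imputed end can fall before the start.

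At stake are the concomitant-medication summaries and the derived end days. SAP 11.2 reclassifies non-ocular drugs that could affect cell count or pain as ocular, for both eyes. A misdated systemic drug of that kind could therefore appear as a study-eye medication in the tables a reader would use to judge confounding.

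**Working it through.** The plan gives no figure to reproduce here, so the three bullets were applied literally.

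**Worked example.** Assume first dose 10 Sep 2019 (Day 1) and last dose 23 Sep 2019 (Day 14).

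| Record | Known part of end date | Imputed end | Result |
|---|---|---|---|
| Stopped before Visit 1, ongoing = No | none | 23 Sep | 13 days after first dose |
| True stop 2 Sep | Sep 2019 | 23 Sep | 13 days after first dose |
| True stop in Aug | 2019 | 23 Sep | 13 days after first dose |
| True stop in Aug | Aug 2019 | 31 Aug | correctly before first dose |
| Start 27 Sep (Day 18), ended in Sep, ongoing = No | none, 2019, or Sep 2019 | 23 Sep | 4 days before the start |

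If the last dose falls on Day 15, the imputed date is 24 Sep and the same rows fail.

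**Exposed window after the last dose.** At nominal Visit 7 it is 22 − 14 = 8 of 22 days (36%), or 22 − 15 = 7 of 22 (32%). Over the Day 20 to 24 window it is 6 to 10 days, or 5 to 9. These are shares of calendar days, not of records.

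**Already-stopped medications: share with an imputed end on or after first dose.** Let g be the days from true stop to first dose. The shortest g is 0 + 1 + 1 = 2 (stop at Visit 1, Visit 1 one day before surgery, first dose one day after). The longest is 30 + 28 + 1 = 59. Assume g uniform on 2 to 59 (58 values, mean 30.5), first doses spread over the year, and a mean month of 365/12 = 30.42 days.

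- Fully missing, ongoing = No: 100%, by construction.
- Day and month missing: wrong when stop and first dose share a year: 1 − 30.5/365 = 92%.
- Day missing: wrong when stop and first dose share a month. Summing 1 − g/30.42 over g = 2 to 30 gives 29 − 464/30.42 = 13.75, and 13.75/58 = 24%.

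The 24% has two parts. The last-dose default needs the stop in the last-dose month. Summing 1 − (g + 13)/30.42 over g = 2 to 17 gives 16 − 360/30.42 = 4.17, and 4.17/58 = 7%. The other 17 points come from the month-end default, when the stop falls in the first-dose month and the last dose in the next. Both branches lack the same check.

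With Visit 1 uniform 1 to 28 days before surgery and the stop uniform 0 to 30 days before Visit 1, the day-missing share is about 16%. With Visit 1 at 1 to 14 days it is about 27%.

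**Post-dose records: share with the end before the start.** Assume onset uniform on Days 15 to 22 (1 to 8 days after last dose, mean 4.5) and true end 0 to 3 days later (mean 1.5). The end is then on average 6 days after the last dose.

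- Fully missing, ongoing = No: 100%.
- Day and month missing: 1 − 6/365 = 98%.
- Day missing: 1 − 6/30.42 = 80%.

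With durations of 1 to 5 days the day-missing share is about 75%. If study drug stops on Day 4 and onset is uniform on Days 5 to 22, it is about 58%.

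**The case against.** The strongest reply is that little of this reaches a result.

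- SAP 14.1 defines treatment emergence by onset or worsening. Its summaries are counts by class, term, relatedness, expectedness, seriousness and severity; none visibly uses an end date. This stands: an end before the start gives an impossible end study day, not a wrong event count.
- The prior and concomitant definitions in SAP 11.2 are redacted. This stands. A reader might infer that stopped medications are definitely counted as concomitant, but the documents do not show it.
- A reader might also infer that every missing stop date goes to the last dose. That is too broad. Fully missing dates with the ongoing flag missing or Yes are left alone, and a month-only date outside the last-dose month goes to month end.
- Washed-out steroids, NSAIDs and analgesics are unlikely to lack stop timing, because sites need it to confirm Exclusion 5. This lowers the likely count, but Protocol 9.3 asks for all medications, not only these classes.
- Edit checks and queries (SAP 6.1) and the blinded medication review (SAP 13.1.2) precede lock. They may reduce the number of incomplete records, but neither is described as correcting an imputed date.
- Extending an unknown stop through treatment is a conservative convention. That is defensible when nothing more is known. It is not when the record shows the drug had already stopped, or when the result precedes a known start.

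**Conclusion.** Wrong as written, with limited reach. The text of SAP 8.2.1 is unredacted, and its literal application gives values that contradict the record's own known facts. The fault is a stated rule, not a missing detail.

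The effect falls on concomitant-medication summaries and derived end days. The first part depends on concomitant meaning use on or after first dose. Efficacy conclusions and treatment-emergent event counts might seem to be at risk, but nothing visible supports that: event status rests on onset, SAP 13.2.5 identifies rescue medication by an eCRF question, and no end date enters the visible primary endpoint derivation.

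The 100% figures restate the rule for fully missing dates and are not a frequency of error in the trial. The month-only shares rest on the uniform-timing assumptions shown. The number of records with incomplete end dates is not given, so the absolute count is unknown and probably small.

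**What to change.** Amend SAP 8.2.1 to impute in this order:

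1. For a medication recorded at Visit 1 as already discontinued, cap the imputed end date at the Visit 1 date, within any reported month or year.
2. Then impute any missing or partial start date, under all three start-date bullets, so that it is not later than the known or imputed end date.
3. For all other records, do not let an imputed end date precede the known start date. Where the last-dose default applies, use the later of the start date and the last dose date, within any reported month or year. Set no cap at study exit that would override a reported end month, since Protocol 10.5 follows adverse events until resolved or stabilized.

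Step 2 is needed because two start-date bullets ignore the end date. Take a start reported only as Sep 2019, Visit 1 on 5 Sep and first dose on 10 Sep. The current start rule gives 10 Sep, after the capped end of 5 Sep. With step 2 the start falls on or before 5 Sep.

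The cost is a few sentences and a small programming change before database lock. The sponsor should confirm that the data identify medications already stopped at Visit 1; no such eCRF field is visible. The downside is that a medication wrongly recorded as stopped at Visit 1 would be classed as prior.

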8.2.2 MISSING EFFICACY DATA

The primary analyses of all efficacy data will use [REDACTED] to impute missing data; data for visits after a subject is discontinued for lack of efficacy or receives rescue medication will be imputed as failures for success/failure endpoints and will be imputed using [REDACTED] for other endpoints. Additional sensitivity analyses based on alternate handling of missing values will be conducted, and described in further detail in Section 13.1.1.

8.2.3 MISSING SAFETY DATA

For all safety variables, missing data will not be imputed, observed values will be presented.

8.3 Definition of Baseline

Baseline is defined as [REDACTED]

[REDACTED]

8.4 Data Analysis Conventions

All data analysis will be performed by SDC after the study is completed and the database has been locked. After the study database has been locked and any other prerequisites for unmasking are met (e.g. all protocol deviations have been classified as major or minor), unmasking will be done for the purpose of the primary analysis, and all planned tables, listings, and figures (TLF) will be generated.

Statistical programming and analyses will be performed using SAS® version 9.4 or higher. Output will be provided in rich text format (RTF) for tables and portable document format (PDF) for TLF using landscape orientation. All study data will be listed by subject, treatment, and visit (as applicable) based on all randomized subjects unless otherwise specified (e.g. demography data, which is also captured for screen failure subjects).

Summaries for continuous and ordinal variables will include the number of observations (n), arithmetic mean, standard deviation (SD), median, minimum, and maximum. Minima and maxima will be reported with the same precision as the raw values; means and medians will be presented to one additional decimal place than reported in the raw values. Standard deviations will be presented to two additional decimal places than reported in the raw values. Summaries for discrete variables will include counts and percentages. All percentages will be rounded to one decimal place (i.e. XX.X%). Differences between active treatment groups and placebo (vehicle) will be calculated as active minus placebo and change from baseline will be calculated as follow-up visit minus baseline.

Dates within subject data listings will be presented based on ISO 8601 standard, as DD-MMM-YYYY.

All efficacy analyses will use a [REDACTED]

[REDACTED]

[REDACTED]

[REDACTED]

Unless otherwise specified, summaries will be presented by treatment group and (where applicable) eye and visit. Analysis by visit will be based on nominal visit identifier. Data from unscheduled visits, unscheduled time points, or unplanned repeat assessments will be included in the data listings. In general, these data will be excluded from the summary tables unless otherwise specified.

Efficacy summaries by treatment group will include the 3 protocol defined treatment groups. Summaries of subject disposition and baseline characteristics will include additional subject groupings defined as:

■ [REDACTED]

■ [REDACTED]

For multiple imputation analyses where a seed may be specified, the seed will be set to 8-digit numeric value corresponding to the database lock date in YYYYMMDD format (eg, 20190901). If multiple seeds are needed within a program, the seed will be based on a 9-digit numeric consisting of the database lock date in YYYYMMDD format concatenated by an additional integer denoting the invocation number (eg, the first invocation would be 201909011, second would be 201909012). [REDACTED]

[REDACTED]

[REDACTED]

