concentration of dexamethasone from DexNP treatment was still 10-times higher than what was observed with Maxidex® treatment. These results demonstrate that dexamethasone, complexed with CD nanoparticles, elicits a higher concentration and longer duration of action in the tear fluid than the currently available product, Maxidex®. Importantly, DexNP was well tolerated by the subjects and no serious adverse events (SAEs) were observed.

A study conducted by Saari et al. ([Saari, Nelimarkka et al. 2006](#)) evaluated the efficacy of an eye drop containing 0.7% dexamethasone-CD suspension, applied once daily, compared to a 0.1% dexamethasone sodium phosphate eye drops, applied three times daily for the treatment of post-operative inflammation after cataract surgery. The dexamethasone-CD suspension was shown to be safe and more effective in treating post-operative inflammation, after once daily dosing, than 0.1% dexamethasone sodium phosphate eye drops applied three times daily.

In the human studies with DexNP to date, DexNP was well tolerated and the only AE reported has been a modest rise in intraocular pressure (IOP), a known side effect of dexamethasone use, which subsided following discontinuation of DexNP in all cases ([Kristinsson, Fridriksdottir et al. 1996](#)) ([Johannesson, Moya-Ortega et al. 2014](#)) ([Saari, Nelimarkka et al. 2006](#)) ([Tanito, Hara et al. 2011](#)) ([Ohira, Hara et al. 2015](#)) ([Krag and Hessellund 2014](#)) ([Shulman, Johannesson et al. 2015](#)).

Building on the enhanced ocular penetration of DexNP, as well as its favorable efficacy results and safety profile, Oculis has developed an updated formulation, OCS-01, consisting of water soluble 1.5% Dexamethasone- γ CD complexes to treat post-surgical inflammation.

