12.2 Treatment Exposure

[REDACTED]

[REDACTED]

[REDACTED]

Although not captured directly on the CRF, additional variables related to study drug administration will also be derived for summarization:

- Study drug interruption (yes/no), where interruptions will be identified via presence of a TEAE where action taken with study drug was marked as 'drug interrupted' or a protocol deviation indicating study drug was interrupted
- Premature discontinuation of study drug (yes/no), where discontinuations will be identified via presence of a TEAE where action taken with study drug was marked as 'drug withdrawn' or a protocol deviation indicating study drug was prematurely discontinued. Subjects who discontinue the study prior to Visit 6 (Day 15) will also be reviewed to verify if study drug was prematurely discontinued or not.
- Study drug completion, defined as those subjects where premature discontinuation of study drug is not equal to 'yes'

A blinded data review will be conducted prior to database lock and unblinding to identify any other cases of study drug interruption or premature discontinuation of study drug which are known to have occurred, but are not identified through the criteria above. The classifications from this final review will be used for analysis.

Subject data listings will be generated to present details of study drug assignment, study drug replacement, as well as first instillation of study medication performed in-clinic on Day 1. Details from the study drug accountability assessment will also be listed.

13. Efficacy Analyses

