13.1 Primary Analysis

The hierarchical primary efficacy measures are the absence of anterior chamber cells [REDACTED]

[REDACTED] and the absence of pain [REDACTED]

The anterior chamber cell count will be recorded as [REDACTED]

[REDACTED] Anterior chamber cell count is assessed for study eye only. Refer to

Table 2 for details.

Table 2. Anterior Chamber Cell Counts and Grade

Ocular pain will be assessed by the patient [REDACTED]

The observed anterior chamber cell count at Visit 6 will be used and categorized for analysis as follows:

- Absence of anterior chamber cells: [REDACTED]
- Presence of anterior chamber cells: [REDACTED]

Within this analysis, missing values for visits after a subject is discontinued for lack of efficacy or values obtained after subject has received rescue medication will be imputed as failures [REDACTED]

[REDACTED] for analysis. For all other missing data, LOCF will be used to impute the missing anterior chamber cell count grade, and the LOCF value will then be categorized for analysis as “cells present” or “cells absent”.

Derivation of the pain score and absence of pain [REDACTED] will follow the same approach for handling of missing data and handling of pain scores obtained following use of rescue medication.

The primary efficacy variables, the absence of anterior chamber cells at [REDACTED] and the absence of pain [REDACTED] will be summarized by [REDACTED]

For each OCS-01 dose (QD and BID) separately, the primary efficacy analyses will [REDACTED]

SAS® code used to generate the [REDACTED]

[REDACTED]

Comparison of OCS-01 QD versus placebo (vehicle) will be conducted in a similar manner, differing only by the treatment arms which are included within the comparison. Testing for each OCS-01 treatment group versus placebo (vehicle) for the absence of pain variable will use similar code.

[REDACTED]
[REDACTED]
[REDACTED]
[REDACTED]
[REDACTED]
[REDACTED]
[REDACTED]

Anterior chamber cell grade in the study eye at Visit 6 (Day 15) will be summarized by [REDACTED]

[figure not shown]
[figure not shown]
[REDACTED]
[REDACTED]

[figure not shown]
[figure not shown]
Ocular pain score at Visit 4 (Day 4) will be summarized by [REDACTED]

The primary efficacy analysis will be conducted using the FAS.

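### Protocol 9.6.2 lets non-compliance or a protocol violation end follow-up, which permits avoidable missing primary data that LOCF then fills

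*SAP*

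**What the plan says.** Protocol 9.6.2 (Discontinued subjects) lists protocol violations among the reasons for discontinuing a subject. It adds that a subject whom the investigator judges non-compliant may be withdrawn from the study. The same section and 6.6 (Withdrawal Criteria) say that a subject who stops study drug or is given rescue stays enrolled and attends every later visit for efficacy and safety. For anyone who does leave early, both sections ask the site to attempt the Visit 7 procedures. By Protocol 9.3 these include cell grade and pain.

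The primary endpoints are absence of cells at Visit 6 (Day 15) and absence of pain at Visit 4 (Day 4) (Protocol 11.5.2). Under Protocol 11.7 and SAP 13.1, values after rescue or after discontinuation for lack of efficacy count as failures. Beyond that, SAP 13.1 says "For all other missing data, LOCF will be used to impute the missing anterior chamber cell count grade", and the pain derivation "will follow the same approach for handling of missing data". The SAP foresees exits before the primary cell visit: in 12.2, "Subjects who discontinue the study prior to Visit 6 (Day 15) will also be reviewed". The purpose there is only to establish whether study drug was stopped early.

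On visit assignment, SAP 8.4 says "Analysis by visit will be based on nominal visit identifier". It puts unscheduled and repeat data in the listings and adds "In general, these data will be excluded from the summary tables unless otherwise specified".

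**The concern.** A subject who abandons the drops altogether still gives a measured primary value, while one who uses them irregularly may be taken out of the study and give none. Irregular dosing does not stop a site from grading cells or asking about pain, so this missing value comes from the rule and could be avoided.

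The primary analysis uses the full analysis set (SAP 13.1). If non-compliance is related to tolerability or to how the eye is recovering, and differs between arms, the missingness is informative and LOCF does not correct for it. The judgement also cannot be checked afterwards against compliance data. SAP 12.1 says that individual home doses are not in the clinical database and that compliance will not be summarised.

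A smaller question follows for every early leaver. The exit examination may be the most recent measurement before the target visit, and the legible text does not say under which visit it is filed or whether LOCF is ordered by date.

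**Working it through.** The documents give no figure to reproduce: Protocol 11.3 shows no text, and the figures in SAP 5 are blacked out.

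**1. The rules side by side, for a subject before Visit 6**

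| Situation | Follow-up (Protocol 6.6, 9.6.2) | Visit 6 cell status (Protocol 11.7, SAP 13.1) |
|---|---|---|
| Stops study drug, no rescue | All later visits | Observed |
| Receives rescue | All later visits | Failure |
| Leaves for lack of efficacy | Ends; Visit 7 procedures attempted | Failure |
| Withdrawn for non-compliance or a violation, no rescue | Ends; Visit 7 procedures attempted | Missing, then LOCF |
| Withdraws consent, no rescue | Ends; Visit 7 procedures attempted | Missing, then LOCF |

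The last two rows both lead to LOCF. Consent withdrawal is the subject's right. In the row above it, the protocol itself allows the gap. The same holds for Visit 4 pain when the exit comes before that visit.

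**2. Age of the carried value**

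Protocol 9.3 gives Visit 3 on Day 2, Visit 4 on Day 3-5, Visit 5 on Day 7-9 and Visit 6 on Day 13-17. Age = target visit day minus day of the last scheduled assessment, with no exit examination used.

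- Cells, last seen at Visit 5: 13 − 9 = 4 to 17 − 7 = 10 days.
- Cells, last seen at Visit 4: 13 − 5 = 8 to 17 − 3 = 14 days.
- Pain, last reported at the Visit 3 call: 3 − 2 = 1 to 5 − 2 = 3 days.

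**3. Size**

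Let k be the number of subjects in an arm of n whose carried status differs from the one that would have been observed. The shift in that arm's proportion, in points, is 100 × k / n. The total of about 150 is stated, but the allocation is redacted. I assume 50 per arm, with 60/60/30 as the alternative. No rate of such withdrawals is given, so k is also an assumption, shown from 0 upwards.

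| k | n = 60 | n = 50 | n = 30 |
|---|---|---|---|
| 0 | 0 | 0 | 0 |
| 1 | 1.7 | 2.0 | 3.3 |
| 2 | 3.3 | 4.0 | 6.7 |

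The shift in the treatment difference also depends on which arm the subjects come from, so its direction is unknown.

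**4. The exit examination (minor)**

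Take a subject seen at Visit 5 on Day 8 whose exit examination is on Day 12. If LOCF runs by date, Visit 6 receives the Day 12 grade. If it ran by nominal order, with the examination filed as Visit 7, Visit 6 would receive the Day 8 grade, which is 12 − 8 = 4 days older. If the examination is tabulated as Visit 7 (window Day 20-24), it appears 20 − 12 = 8 days before that window opens. The legible text does not say which applies.

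**The case against.** **On withdrawal.** The passages do not contradict each other. The non-compliance clause is permissive, exit procedures are still attempted, and subjects who stop drug are expressly kept. No number of such withdrawals is given, and there may be none. Protocol 11.7 also plans observed-data, multiple-imputation and tipping-point analyses. All of this stands and keeps the point small. It does not remove it, because sensitivity analyses probe missing values and do not recover them. Keeping such subjects under observation also does not put them into the per-protocol set, since SAP 6.1 has deviations classified and populations determined before analysis.

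**On the exit examination.** A reader might infer from SAP 8.4 that LOCF discards the exit grade. The documents do not support this. Last observation carried forward ordinarily means the latest in time. SAP 8.4 governs by-visit analysis and summary tables, not which values LOCF may carry. A labelling rule may stand in redacted parts of SAP 8.2.2, 8.4, 13.1, 13.1.1 or 14.5, or in the visit schedules, which cannot be read here. This is therefore a request for confirmation, not a proven omission.

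**On eye pressure.** A reader might also infer that Day 22 pressure tables mix on-treatment and off-treatment readings. SAP 8.2.3 says that for safety variables "missing data will not be imputed, observed values will be presented". SAP 3.1 says "Subjects will dose 1 drop in the study eye BID for 14 days". Protocol 3.1 describes a pressure rise "which subsided following discontinuation of DexNP in all cases". A shift in mean pressure does not follow. It would need exit examinations to be filed as Visit 7, which is not stated. Exits on Day 16-17 come after dosing. The vehicle arm receives no dexamethasone. SAP 14.5 is almost wholly redacted. No size can be supported.

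**On unscheduled visits.** Protocol 9.4.2 ties these to adverse events, with assessments at the investigator's discretion. Making all of them LOCF sources would bring event-triggered measurements into a primary endpoint, so that is not proposed.

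**Conclusion.** The point holds as a low-cost improvement. Protocol 9.6.2 permits study withdrawal for non-compliance or a protocol violation, although 6.6 and 9.6.2 keep subjects who stop drug or receive rescue under assessment. This allows avoidable missing values for Visit 4 pain and Visit 6 cells, which LOCF fills unless the subject had rescue or left for lack of efficacy. The effect is unknown in size and direction, probably small and possibly nil. The figure of 2.0 points per changed subject rests on an assumed 50 per arm (1.7 at 60, 3.3 at 30). The number of such subjects is not documented.

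The LOCF order and the label of the exit examination are a secondary matter, limited to the legible text. Analysing by nominal visit is not an error in itself.

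**What to change.** 1. In the protocol, reconcile 9.6.2 with 6.6 so that non-compliance or a protocol violation alone does not end follow-up assessments. Leave withdrawal of consent and the safety provisions as they are. The edit concerns attendance for assessment only and does not touch treatment decisions.
2. In SAP 8.4 or 13.1, unless redacted text already does so, confirm two things. LOCF for the primary endpoints takes the latest examination by date before the target visit, including an early-exit examination, with the rescue and lack-of-efficacy rules unchanged. An early-exit examination outside Day 20-24 is not tabulated as Visit 7, though it would still be listed.

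The cost is one protocol edit and a couple of SAP sentences, with a small derivation if the rule is not already programmed. A few subjects continue visits that are already planned. No assessment is added. An out-of-window exit value would appear in listings and not in the Day 22 summary, which is a minor loss from the tables.
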